8.6.4.6.2 Administration of the IP and After

The following additional procedures are to be conducted and documented at Visit 9 as related to administration of the IP:

- IRT IP assignment
- Administer the fourth SC dose of the IP
- Collect information on AEs, including local tolerability assessment
- Remind subject to collect FMV urine samples for 3 days leading up to the next visit and to arrive after a minimum 6-hour fast

8.6.5 Follow-up

8.6.5.1 Follow-up Visit 10 (Week 16, Day 113)

The following procedures are to be conducted and documented at Visit 10:

- Perform serum or urine pregnancy test (FCBP only)
- Perform abbreviated physical examination
- Measure vital signs (BP in triplicate)
- Measure weight
- Perform 12-lead ECG (triplicate)
- Collect blood samples for the following:
 - Standard hematology and biochemistry testing
 - Troponin-I and BNP
 - HbA1c

- Immunogenicity
- Biomarker analysis
- Collect trough PK blood sample
- Collect urine samples for the following:
 - FMV (for Days 111, 112, and 113)
 - Morning midstream
- Collect information on AEs, including local tolerability assessment
- Collect information on concomitant therapies
- Remind subject to collect FMV urine samples for 3 days leading up to the next visit

8.6.5.2 End of Study (Week 24, Day 169)

The following procedures are to be conducted and documented at EOS:

- Perform serum or urine pregnancy test (FCBP only)
- Perform complete physical examination
- Measure vital signs (BP in triplicate)
- Measure weight
- Perform 12-lead ECG (triplicate)
- Collect blood samples for the following:
 - Standard hematology and biochemistry testing
 - Troponin-I and BNP
 - HbA1c
- Collect trough PK blood sample
- Collect urine samples for FMV (for Days 167, 168, and 169)
- Collect information on AEs
- Collect information on concomitant therapies

9 Adverse Events

9.1 Definitions

9.1.1 Adverse Event

As per the ICH Topic E2A (Clinical Safety Data Management: Definitions and Standards for Expedited Reporting), an AE is any untoward medical occurrence in a patient or clinical investigation subject administered a pharmaceutical product, and which does not necessarily have a causal relationship with this treatment. An AE can, therefore, be any unfavorable and unintended sign (including an abnormal, clinically significant laboratory finding), symptom, or disease temporally associated with the use of a medicinal (investigational) product, whether or not considered related to the medicinal (investigational) product.

The period of observation for AEs extends from the time the subject gives informed consent until the end of study (see [Section 9.4](#) for further details).

Adverse events may include the following:

- Exacerbation (ie, an increase in the frequency or severity) of a pre-existing condition. Illness present before study entry should be recorded in the medical history section of the eCRF and only be reported as an AE if there is an increase in the frequency or severity of the condition during the study
- A clinical event occurring after consent but before IP administration
- Intercurrent illnesses with an onset after administration of IP

Adverse events do not include:

- Events identified at Screening that meet exclusion criteria
- Medical or surgical procedures (the condition that leads to the procedure is the AE)
- Situations where an untoward medical occurrence has not taken place. For example:
 - Planned hospitalizations due to preexisting conditions, which have not worsened
 - Hospitalizations that occur for procedures not due to an AE (eg, cosmetic surgery)
 - Hospitalizations for a diagnostic procedure where the hospital stay is less than 24 hours in duration or for normal management procedures (eg, chemotherapy)

- Overdose of IP or any concomitant therapy that does not result in any adverse signs or symptoms

For laboratory safety parameters, any instances of absolute values being outside the reference range or changes at any visit after study start that are considered by the Investigator as clinically significant must be recorded in the eCRF as AEs. In addition, at the Investigator's discretion, any changes or trends over time in laboratory parameters can be recorded in the eCRF as AEs if such changes or trends are considered to be clinically relevant, even if the absolute values are within the reference range.

Laboratory findings do not need to be reported as AEs in the following cases:

- Laboratory parameters already beyond the reference range at screening, unless a further increase / decrease can be considered an exacerbation of a preexisting condition
- Abnormal laboratory parameters caused by mechanical or physical influences on the blood sample (eg, in vitro hemolysis) and flagged as such by the laboratory in the laboratory report
- Abnormal parameters that are obviously biologically implausible (eg, values that are incompatible with life or outside the measuring range)
- An abnormal laboratory value that cannot be confirmed after repeat analysis, preferably in the same laboratory (ie, the previous result could be marked as not valid and should not necessarily be reported as an AE)

9.1.2 Serious Adverse Event

An SAE is defined as any untoward medical occurrence that at any dose:

- **Results in death** – The event must be the cause of death for the SAE to meet this serious criterion
- **Is life-threatening** – The term “life-threatening” refers to an event in which the subject was at risk of death at the time of the event; it does not refer to an event that hypothetically might have caused death if it had been more severe

- **Requires in-patient hospitalization or prolongation of existing hospitalization** – CSL considers “hospitalization or prolongation of existing hospitalization” for at least 24 hours as the defining criterion for an SAE. Hospital admissions for planned surgery or for normal disease management procedures (eg, chemotherapy) are not considered as defining criteria for SAEs
- **Results in persistent or significant disability or incapacity**
- **Is a congenital anomaly or birth defect**
- **Is medically significant** – A medically significant event is defined as an event that does not necessarily meet any of the SAE criteria, but which is judged by a physician to potentially jeopardize the subject or require medical or surgical intervention to prevent 1 of the above outcomes listed as an SAE criterion

Adverse events that do not fall into the above categories are defined as nonserious AEs.

9.1.3 Adverse Events of Special Interest

Adverse events of special interest are injection site reactions ([Section 9.1.3.1](#)), increase in serum creatinine ([Section 9.1.3.2](#)), albuminuria ([Section 9.1.3.3](#)), or baseline blood pressures ([Section 9.1.3.4](#)), and cardiac AEs ([Section 9.1.3.5](#)).

The safety monitoring plan and guidance for assessing and managing AESIs were developed based on the available nonclinical and clinical data with CSL346, and the expected baseline renal function in the study population.

Guidance for assessing and managing renal and cardiac risk were developed to allow for careful observation of subjects enrolled in the study for increases in SCr, increases in albuminuria, increases in BP, and changes in cardiac parameters.

When an AE satisfies the criteria for an AESI detailed below, the Investigator will assess the AESI’s potential relationship to the IP. The AE/SAE/AESI eCRF is to be completed, providing additional detail about the AESI. If the Investigator assesses the AESI as not related to treatment with the IP, other known or suspected causes of the AESI should be recorded (eg, noncompliance with SOC medications).

All events will be reviewed with the IDMC during regularly scheduled safety review meetings.

The Investigator must report any AESI using the AE/SAE/AESI eCRF. Reporting requirements for AESIs are detailed in [Section 9.6.2](#).

9.1.3.1 Injection Site Reactions

Injection site reactions are an identified risk with the SC administration of CSL346.

[figure not shown]
To closely monitor these events, all injection site reactions should be considered AESIs and the AE/SAE/AESI eCRF must be completed.

For mild injection site reactions (defined below) that are deemed unacceptable by the subject or Investigator, and would otherwise lead to discontinuation of the IP, stepwise modification of the volume and / or dose administered should be attempted, as described in [Figure 3](#) and [Table 11](#).

A *mild* injection site reaction is defined as follows:

Tenderness at a site of administration, with or without associated symptoms (eg, warmth, erythema, itching). Mild to moderate pain at a site of administration that resolves within 48 hours.

Figure 3 Flowchart for Stepwise Modification of Investigational Product Administration Due to Unacceptable Mild Injection Site Reactions

IP = investigational product; ISR = injection site reaction; SC = subcutaneous.

Note: An unacceptable mild ISR is any event that meets the definition provided that, in the absence of alternative dosing provisions, would result in the subject's discontinuation from further IP administration.

Table 11 Stepwise Dosing Modification of Investigational Product Administration for Unacceptable Mild Injection Site Reactions

	Randomized Treatment Arm		
	8 mg/kg Arm	16 mg/kg Arm	Placebo Arm
Starting Dose			
Dose Level	8 mg/kg	16 mg/kg	Placebo
SC Infusion Volume	20 mL	20 mL	20 mL
Step 1 (≥ Second SC Dose)			
Dose Level	8 mg/kg	16 mg/kg	Placebo
SC Infusion Volume	2 × 10 mL	2 × 10 mL	2 × 10 mL
Step 2 (≥ Third SC Dose)			
Dose Level	8 mg/kg	8 mg/kg	Placebo
SC Infusion Volume	2 × 5 mL	2 × 5 mL	2 × 5 mL
Step 3	Discontinue further dosing		

SC = subcutaneous.

Subjects are randomized into 1 of 3 treatment arms: CSL346 8 mg/kg treatment arm, CSL346 16 mg/kg treatment arm, or placebo treatment arm. At the starting dose, subjects randomized to the 16 mg/kg treatment arm receive a more concentrated dose than subjects in the 8 mg/kg treatment arm because both doses are administered in the same total volume (20 mL). The infusion volume (Figure 3), dose and / or the concentration (Table 11) of IP may be adjusted if there are mild injection site reactions. If a subject has mild injection site reactions at the starting dose that are deemed unacceptable by the subject or Investigator, and would otherwise lead to discontinuation of the IP, proceed to Step 1.

In Step 1, the dose, which is the same as the dose level and concentration of the starting dose, is administered as 2 infusions of 10 mL instead of a single infusion of 20 mL. This adjustment will help determine if reducing the volume infused at a given site reduces the occurrence of injection site reactions. If, after Step 1, the subject continues to have mild injection site reactions that are deemed unacceptable by the subject or Investigator, and would otherwise lead to discontinuation of the IP, contact the Study Medical Monitor to discuss and document the appropriate action to be taken for that subject. If the Medical Monitor approves, proceed to Step 2.

Step 2 is as follows:

- Subjects randomized to the 8 mg/kg treatment arm are to be administered 8 mg/kg CSL346 in two 5 mL SC infusions, halving the total infusion volume and thereby doubling the concentration of CSL346 administered in the previous step
- Subjects randomized to the 16 mg/kg treatment arm are to be administered 8 mg/kg CSL346 in two 5 mL SC infusions, halving the dose level and total infusion volume and thereby maintaining the same concentration of CSL346 administered in the previous step

These adjustments will help determine if reducing the total dose infused at a given site reduces the occurrence of injection site reactions.

If, after Step 2, the subject continues to have mild injection site reactions that are deemed unacceptable by the subject or Investigator, and would otherwise lead to discontinuation of the IP, contact the Study Medical Monitor to discuss and document the appropriate action to be taken for that subject. If the Medical Monitor approves, then move to Step 3 and discontinue further dosing with IP. Every effort should be made to continue the subject's participation in Follow-up Visits even if the IP is discontinued.

For any injection site reaction that exceeds the definition of mild, either in duration or severity of symptoms, the Study Medical Monitor must be contacted to discuss and document the rationale for continuing administration of the IP at a decreased total SC infusion volume and / or dose, or discontinuing further dosing.

9.1.3.2 Serum Creatinine

The criteria for increases in SCr due to AKI are based on a definition of AKI that incorporates absolute changes in SCr over a 24- to 48-hour period (Waikar and Bonventre, 2009). The percent changes in SCr after severe AKI are highly dependent on baseline kidney function. In contrast, the absolute increases in SCr are nearly identical across the spectrum of baseline kidney function. Conservative criteria were identified to trigger a comprehensive evaluation that balances the safety of subjects enrolled in the study with small changes in SCr expected due to intrasubject variability.

An SCr AESI is defined as a confirmed increase from Baseline of at least 0.3 mg/dL. All cases meeting the criteria shown in Table 12 will be specifically reviewed with the IDMC during regularly scheduled safety review meetings.

Table 12 **Increases in Serum Creatinine**

Serum Creatinine – Increase from Baseline (Confirmed)	Investigator Assessment	Action
≥ 0.3 to < 0.7 mg/dL (≥ 26.5 to < 61.9 μmol/L)	Expected changes due to IP-related activity	Continue IP with increased monitoring
≥ 0.7 mg/dL (≥ 61.9 μmol/L)	Reversible episode of AKI unrelated to IP	Withhold IP until serum creatinine returns to baseline
	IP related	Permanently discontinue IP

AKI = acute kidney injury; IP = investigational product.

If a subject has an increase in SCr that meets criteria outlined in Table 12 at any visit while receiving IP, the Investigator will complete an eCRF reviewing possible causes of AKI not related to IP such as volume depletion, urinary tract infection, and exposure to a nephrotoxic agent. Any identified possible reversible causes of AKI not related to IP will be addressed promptly according to local standards of care. A second measurement will be obtained as soon as possible within a maximum of 1 week. If the specified increase is confirmed, the Investigator will obtain a third SCr value within 1 week and update the eCRF.

The Investigator will contact the Medical Monitor who will assist with evaluation and determination of appropriate action to be taken. This consultation will help discern signs of

possible AKI not related to IP from hemodynamically mediated effects on SCr / eGFR potentially associated with IP-related activity, reversible causes of AKI not related to IP or from renal intrinsic injury related to IP.

The trending changes in SCr over multiple time points will be evaluated in the context of changes in albuminuria, BP, and other clinical parameters over that period, and recommendations will be provided to the Investigator. This may include guidance for heightened monitoring of renal parameters, clinical maneuvers to reverse reversible causes of AKI not related to IP (eg, treat active urinary tract infection), temporary interruption of IP, or permanent discontinuation from IP. The Medical Monitor will be available 24 hours a day and must be consulted by the Investigator; subsequently, the Investigator will make the decision to either administer the next monthly dose of IP or permanently discontinue a subject from treatment. Note that every effort will be made to continue the subject's participation in Follow-up Visits even if IP administration is stopped.

9.1.3.3 Albuminuria

The criteria for increases in albuminuria were derived from an analysis of biological variability in albuminuria levels in subjects with CKD (Waikar et al, 2018). Within subject CV is approximately 30% for FMV urinary ACR and is comparable across the range of baseline values. The high intrasubject variability makes it difficult to distinguish random variability from an adverse effect.

An albuminuria AESI, based on the geometric mean of ACR values from up to 3 FMV samples collected at that on-treatment time point, is a confirmed ≥ 2 -fold increase (doubling) from Baseline with additional evidence suggesting AKI. Additional evidence suggesting AKI includes observations such as acute changes in BP or serum creatinine and are described in the study's Manual of Operations.

The following sequence is recommended for evaluation and follow-up:

- Initial flag received from central laboratory for ACR value $\geq 2x$ baseline value:
 - Site orders urinalysis to be performed locally and urine culture if indicated
 - Obtains 3 additional FMV urine samples for confirmation of increased ACR value by central laboratory
- If confirmed (second ACR flag received from central laboratory):

- Performs novel coronavirus 2019 (COVID-19) polymerase chain reaction test, if indicated
- Repeats hematology (white blood cells and differential, platelet count) and blood chemistry (including blood urea nitrogen analysis at central laboratory)
- Obtains vital signs, including body weight and triplicate measurements of BP
- Questions subject about adherence to, or changes in, concomitant medications, and other potential changes to the subject's routine (eg, atypical diet or exercise)
- If additional evidence suggesting AKI is identified, the definition of an albuminuria AESI is met.
 - Completes the AE/SAE/AESI eCRF to indicate an AESI has occurred
 - Updates the AE/SAE/AESI eCRF with any new information (eg, changes in, or missed doses of concomitant medications, AEs)

The Investigator will contact the Medical Monitor who will assist with evaluation and determination of appropriate action to be taken. This may include guidance for heightened monitoring of renal parameters, clinical maneuvers to reverse reversible causes not related to IP, temporary interruption of IP, or permanent discontinuation from study treatment. The Medical Monitor will be available 24 hours a day and must be contacted for consultation before the Investigator decision to either administer the next monthly dose of IP or permanently discontinue a subject from treatment. Note that every effort will be made to continue the subject's participation in Follow-up Visits even if IP is stopped.

All cases meeting these criteria will be specifically reviewed with the IDMC during regularly scheduled safety review meetings.

9.1.3.4 Blood Pressure

An AESI related to BP is defined as an observed SBP \geq 180 mmHg and / or DBP \geq 120 mmHg or an increase from Baseline in either SBP or DBP \geq 20 mmHg and greater than 160 / 105 mmHg. In subjects presenting with a SBP \geq 180 mmHg or a DBP \geq 120 mmHg, the Investigator will assess the subject for evidence of a hypertensive emergency, treat promptly according to the SOC, and if the subject is confirmed to have a hypertensive emergency, complete an SAE form. Evidence of end organ damage includes hypertensive encephalopathy, retinal hemorrhages, papilledema, or acute and subacute kidney injury. The Investigator should not administer the IP and must contact the Medical Monitor for consultation as soon as

possible and within 1 business day. After consultation with Medical Monitor, the IP may be permanently discontinued or the IP may be resumed with increased monitoring of BP with unscheduled visits as dictated by SOC. Note that every effort will be made to continue the subject's participation in all study visits even if the IP is stopped.

If a subject has an observed SBP ≥ 180 mmHg and / or DBP ≥ 120 mmHg or an increase from Baseline in either SBP or DBP ≥ 20 mmHg and $> 160 / 105$ mmHg, and the subject has minimal or no symptoms and the increase confirmed at least 30 minutes later, the Investigator should intervene according to SOC as follows:

- If a cause for the rise in BP unrelated to IP administration **is not identified**, the IP may not be administered and the Investigator must contact the Medical Monitor for consultation as soon as possible and within 1 business day. After consultation with the Medical Monitor, the IP may be permanently discontinued or the IP may be resumed with increased monitoring of BP with unscheduled visits as dictated by SOC. Note that every effort will be made to continue the subject's participation in all study visits even if the IP is stopped.
- If a cause for the rise in BP unrelated to IP administration **is identified** (eg, medication noncompliance or other extenuating circumstances), the cause should be addressed and the IP may then be administered. The Investigator should complete an eCRF reviewing possible causes of elevated BP not related to IP. The subject should have unscheduled visits with increased monitoring of BP as dictated by SOC. If the SBP does not return to < 180 mmHg or the DBP does not return to < 120 mmHg, the Investigator must contact the Medical Monitor for consultation before the Investigator makes a decision to either administer the next monthly dose of IP or discontinue a subject from treatment. Administration of IP may continue with increased monitoring of BP as dictated by SOC. Note that every effort will be made to continue the subject's participation in all study visits even if IP is stopped.

All cases will be specifically reviewed with the IDMC during regularly scheduled safety review meetings.

The indicated increases in BP will be measured according to the protocol-specified procedure.

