Differences in potency between the mouse 2H10 antibody and CSL346 were calculated using data from a cell-based assay of VEGF-R1 activity [Mould et al, 2005]. The half maximal inhibitory concentrations of 2H10 in the presence of mouse VEGF-B (20 nM) and of CSL346 in the presence of human VEGF-B (1.25 nM) were 3 nM and 0.18 nM, respectively. The ratio

of these values (16.7) was used to correct for the observed effective concentration of 2H10 in mice and predict a target C_{trough} of CSL346 in humans. With the 16.7 adjustment for potency, a target CSL346 C_{trough} of 11 $\mu\text{g}/\text{mL}$ was calculated. In a direct binding enzyme-linked immunosorbent assay, the half maximal effective concentration (EC_{50}) of 2H10 on 1 $\mu\text{g}/\text{mL}$ mouse VEGF-B was 3.21 nM and the EC_{50} of CSL346 on 1 $\mu\text{g}/\text{mL}$ human VEGF-B was 0.257 nM. When using the ratio of these values (12.5) to correct for the concentration in mice, a target C_{trough} of 14.4 $\mu\text{g}/\text{mL}$ was calculated. Selection of the doses was based on the 14.4 $\mu\text{g}/\text{mL}$ target C_{trough} , as the direct binding assay provides a more accurate measure.

Considering the prolonged half-life (approximately 30 days), up to 5 months of monthly administration would be required to reach steady state with SC administration. Therefore, a single loading dose will be administered by IV infusion on Day 1 (Visit 4), followed by an SC infusion on Day 1 (Visit 4) to reach approximate steady state CSL346 concentrations earlier in the Treatment Period. To maintain target serum concentrations, IP will be administered by SC infusion every 4 weeks thereafter.

[figure not shown]

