4.1.3 Randomization Criteria

To be randomized into the study, subjects must meet the following Randomization Criteria at Visit 3 (Day -7) and Visit 4 (Day 1):

1. $SBP \leq 150$ mmHg and $DBP \leq 100$ mmHg at Visit 3 (Day -7) and Visit 4 (Day 1). If the subject's BP at Visit 3 (Day -7) or Visit 4 (Day 1) does not satisfy this criterion, randomization / treatment should be delayed and FMV urine samples discarded. The Investigator should ensure the subject is compliant with concomitant antihypertensive medications and can repeat this BP evaluation within 3 to 10 days of the failed criterion. The subject will be instructed to collect 3 additional FMV urine samples.
 - If a subject satisfies the BP criterion at the rescheduled visit, the subject can be randomized.
 - If a subject fails to satisfy the BP criterion at the rescheduled visit, the subject will be considered a Lead-in failure (discontinued from study) and will not be re-screened
 - If a subject fails to satisfy the BP criterion at any 2 visits (including Visit 3, Visit 4, and the rescheduled visit), the subject will also be considered a Lead-in failure (discontinued from study) and will not be re-screened

2. Change in SCr from Visit 2 (Day -21) to Visit 3 (Day -7) ≤ 0.3 mg/dL (26.5 $\mu\text{mol/L}$) by central lab assessment. Subjects who do not satisfy this criterion may have 1 repeat SCr test performed at an unscheduled visit within 1 week after Visit 3 (Day -7); for these subjects, the randomization criterion will be evaluated based on change in SCr from Visit 3 (Day -7) to the unscheduled visit (≤ 0.3 mg/dL change by central lab assessment). Subjects who qualify must return for randomization (Visit 4 / Day 1) within 1 week after the unscheduled visit. Subjects who do not qualify will be considered a Lead-in failure (discontinued from the study) and will not be re-screened.
3. Troponin-I levels \leq URL at Visit 3 (Day -7).

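### Protocol 9.1.3.4 gives two different dosing rules for a subject with confirmed SBP >= 180 or DBP >= 120 mmHg, minimal or no symptoms and an identified cause unrelated to the product

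*Protocol*

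**What the plan says.** All the text at issue is in Protocol 9.1.3.4, Blood Pressure.

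- **First paragraph.** For subjects who present with SBP >= 180 or DBP >= 120 mmHg, the Investigator looks for a hypertensive emergency, treats to standard of care, and completes an SAE form if an emergency is confirmed. After a sentence listing signs of end organ damage comes the dosing instruction: "The Investigator should not administer the IP and must contact the Medical Monitor for consultation", with contact due within 1 business day. IP may be stopped for good or resumed after that consultation.
- **Second paragraph.** It names the 180/120 range again, together with the lower limb (a rise of at least 20 mmHg to above 160/105). It adds two conditions: "the subject has minimal or no symptoms and the increase confirmed at least 30 minutes later". Two bullets follow.
- **'Is not identified' bullet.** IP may not be given, and the Medical Monitor must be contacted on the same timescale as in the first paragraph.
- **'Is identified' bullet.** If a cause unrelated to IP is found, "the cause should be addressed and the IP may then be administered". If pressure does not return below 180 or 120, the Medical Monitor must be contacted "before the Investigator makes a decision to either administer the next monthly dose of IP or discontinue a subject from treatment". The next sentence reads: "Administration of IP may continue with increased monitoring of BP as dictated by SOC".

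**The concern.** A subject in the highest blood pressure tier, with few or no symptoms and a plausible outside cause such as missed tablets, falls under both paragraphs. The first says to hold and consult. The bullet says to deal with the cause and dose. Two sites could each follow the protocol and act differently on the same reading.

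This is a safety instruction, and raised blood pressure is a listed potential risk of CSL346 (Protocol Table 1). The other oversight does not have to come before the dose: AESI entry is due within 24 hours (9.6.2), and IDMC review takes place at scheduled meetings. Nothing in the Steering Committee's role (3.6.2) requires its input before that dose.

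**Working it through.** **Side by side.** Take a subject at 186/100 at Week 8, without symptoms, confirmed 30 minutes later, with missed antihypertensive doses identified and addressed.

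| Question | First paragraph | 'Is identified' bullet |
|---|---|---|
| Does it apply? | Yes: SBP >= 180, no symptom condition | Yes: SBP >= 180, minimal symptoms, confirmed, cause found |
| May IP be given now? | No | Yes, once the cause is addressed |
| Medical Monitor first? | Yes, always | Only if BP does not return below 180/120 |

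**Is the first paragraph's hold conditional?** The only conditional clause concerns a confirmed hypertensive emergency, and it governs the SAE form. The hold is a separate sentence with no condition.

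**Does the 'does not return' sentence remove the conflict?** No. Read generously, 'next monthly dose' is the dose now pending, so a subject still at or above 180/120 would be discussed before it. A subject whose pressure has fallen back could still be dosed without the consultation that the first paragraph requires. Read less generously, it is the dose four weeks later, and the pending dose has no consultation at all.

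**Neighbouring rules.** For creatinine, "The Medical Monitor will be available 24 hours a day and must be consulted by the Investigator" (9.1.3.2) before the Investigator decides on the next dose. The albuminuria section (9.1.3.3) also puts consultation before that decision.

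**How often?** The documents give no blood pressure distribution, so every blood pressure input below is an assumption, apart from the randomization limits and the dosing visits:

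- usual BP 135/78 mmHg, between-subject SD 11/8;
- visit-to-visit SBP SD 8, 10, 12 or 15, with DBP visit SD 0.6 times that;
- SBP/DBP correlation 0.6 between and within subjects;
- reading error SD 5 (SBP) and 3 (DBP), drawn afresh for the first and the confirming reading;
- two pre-dose visits at SBP <= 150 and DBP <= 100 (Protocol 4.1.3), then the dosing visits at Weeks 4, 8 and 12;
- drug effect either none or +10 mmHg SBP with +6 mmHg DBP.

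The event is both readings at SBP >= 180 or DBP >= 120 at one or more of the three visits. Simulation with about a million or more subjects per scenario gives:

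| Visit SD (SBP) | No drug effect | +10 mmHg SBP | Of 50 CSL346 subjects at +10 mmHg |
|---|---|---|---|
| 8 | 0.002% | about 0.1% | 0.001 x 50 = 0.05 |
| 10 | 0.02% to 0.03% | 0.38% | 0.0038 x 50 = 0.19 |
| 12 | 0.11% to 0.12% | 1.06% | 0.0106 x 50 = 0.53 |
| 15 | not tabulated | about 3.1% | 0.031 x 50 = about 1.5 |

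Ranges show differences between simulation runs. Only the part with an identified unrelated cause meets the conflict. If that share is 25% to 75% (assumed), the visit SD 12 figure becomes 0.53 x 0.25 = 0.13 to 0.53 x 0.75 = 0.40 of 50 subjects. At visit SD 15 it is 1.5 x 0.25 = 0.4 to 1.5 x 0.75 = 1.1.

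**Exposure cost of a hold.** Protocol 3.3.2 gives a half-life of about 30 days. A delay of d days lowers the pre-dose concentration by 1 - 2^(-d/30): 6.7% for 3 days, 10.9% for 5 days, 20.6% for 10 days. The visit windows are 3 days at Week 4 and 5 days at Weeks 8 and 12.

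**The case against.** The strongest reply is that the section can be read coherently. If the first paragraph already held every subject at or above 180/120, there would be no need to repeat that range in the second with an identical hold under 'is not identified'. The hold follows the end-organ-damage sentence. The second paragraph adds conditions and reads naturally as the non-emergency branch. The 'does not return' sentence also shows that subjects at or above 180/120 were expected in the 'is identified' bullet. This is a fair account of what may have been intended. It does not settle the matter, because no words limit the first paragraph to emergencies and none rank the two rules.

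A reader might go further and infer any of the following, which the documents do not support:

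- **That the bullet allows dosing at 180/120 with no safeguard.** The cause must be addressed, and persistently high pressure triggers consultation. BP is measured before each SC dose (8.1.1), so 'next monthly dose' can mean the pending one.
- **That IP should be barred until BP is re-measured below 180/120.** Neither the first paragraph nor the 'is not identified' bullet has such a gate. Putting it only in this bullet would treat a subject with a known outside cause more strictly than one in whom CSL346 is the suspect.
- **That the pre-randomization rule proves the intent.** In 4.1.3, at SBP > 150 or DBP > 100, "randomization / treatment should be delayed and FMV urine samples discarded". That rule also protects the ACR baseline, so it is only a comparison.
- **That fewer than one subject will ever be affected.** This depends on the assumed SDs. At visit SD 15 with +10 mmHg, about 1.5 of 50 CSL346 subjects reach the tier. The model also has random variation only and does not represent missed tablets, the trigger that matters here.

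**Conclusion.** The conflict is real as written but narrow. It covers subjects at or above 180/120 mmHg with minimal or no symptoms, a confirmed reading and an identified unrelated cause. They are told both to wait for the Medical Monitor and that they may be dosed without that contact.

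Severity is minor. On the assumptions above, about 0.002% to 0.12% of subjects would reach the tier with no drug effect (visit SD 8 to 12). With +10 mmHg it is about 0.1% to 1.1% at visit SD 8 to 12, and about 3% at SD 15. These figures show the order of size; they are not forecasts.

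A reader might infer harm to the trial's results, but that does not follow. The blood pressure AESI is defined by the readings (Protocol 9.1.3.4, SAP 11.2), whatever is done about the dose. The ITT analysis of ACR follows a treatment policy strategy (SAP 10.1.1) and keeps the data of subjects with held or missed doses. What is at stake is consistent handling of a rare safety event across sites.

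**What to change.** In the 'is identified' bullet of Protocol 9.1.3.4, directly after the permission to give IP, add:

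> *except that for SBP >= 180 mmHg or DBP >= 120 mmHg the IP is held until the Medical Monitor has been consulted (promptly, and within 1 business day), as in the first paragraph of this section.*

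Keep the 'does not return' sentence and add no fixed BP gate. The bullet then matches the first paragraph and the 'is not identified' bullet. Dosing after addressing the cause alone applies only to the lower limb: a rise of at least 20 mmHg to above 160/105 but below 180/120.

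The cost is one clause, one call to a Medical Monitor who is already available 24 hours a day, and an occasional short delay. A hold of 3 to 5 days lowers the pre-dose concentration by about 7% to 11%. If a hold ended in a missed dose, SAP 16.7 lists that among the reasons for excluding later data from the Per-Protocol set; the ITT primary analysis would keep them.
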